1. To characterize VHA CLCs in terms of alternate measures of hospitalization for long stay and post-acute care Veterans, including Medicare hospitalizations, and to examine regional variations in these rates over the period 2007 thru 2012;
2. (a) To modify, for VHA implementation, and pilot the INTERACT quality improvement program training materials; and (b) To implement the INTERACT quality improvement program as the intervention in 8-15 randomly selected, pair matched CLCs for a 6 month intensive training period and an additional 24 month implementation and data collection period.
3. To conduct a quantitative and qualitative evaluation of the implementation of the INTERACT quality improvement program in order to characterize the fidelity with which CLCs in the intervention pairs participated in training, engaged in regular conference calls, undertook root cause analyses identifying why hospitalizations occurred and used the tools in which they were trained;
4. To test the effect of the implementation of INTERACT as an intervention on the rate of reduction in hospitalizations from CLCs in the intervention as compared to the matched control facilities and to determine via a formalized “structured implicit review” whether the intervention was associated with a reduction in “avoidable” hospitalizations and did not lead to negative outcomes like mortality and ADL decline;
5. To conduct a Budget Impact Analysis of the cost of the intervention relative to the “savings” associated with fewer hospitalizations

B. INTRODUCTION/ BACKGROUND

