Significance to the VHA: In conjunction with our GEC partners, this project is being proposed as one component of a general effort to improve care and enhance the medical capacity of CLC nursing and medical staff. If the INTERACT training program is effective, GEC anticipates expanding investment in the on-line training system and identifying local champions at CLCs across the country and implementing INTERACT. The training of CLC nursing and medical staff in INTERACT is completely compatible with, but expands upon, VHA "culture transformation" efforts. Reducing hospitalizations from CLCs has immediate positive benefits on the experience of Veterans since they would be spared the trauma of unnecessary transfer to hospital. In addition, INTERACT training advances several principles central to culture transformation by promoting Veteran-directed advance care planning and training staff to understand Veteran patterns of daily activities to better identify early warning signs and symptoms of decline.

Impact of Findings on the VHA: We expect that, compared to control-CLCs, intervention -CLCs which fully implement INTERACT will reduce hospitalizations by 20%, identifying avoidable hospitalizations. This figure is lower than the 25% reduction in hospitalization among facilities that were engaged in the INTERACT intervention.[11] Consistent with findings from community NHs, these reductions in hospitalizations will be achieved without increasing mortality or accelerating functional decline. From the VAMC perspective, this means hospital beds will be available for more emergent cases without major increases in VHA costs.

C. STUDY PROCEDURES Overview:

The INTERACT program, training curriculum and tools will be refined to be appropriate for implementation in a VA setting both in relation to standard CLC operating procedures and VHA language and policies.

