[name] will assist the research team in recruiting up to 17 reviewers experienced with CLC care from VA GRECC clinical staff and from VA CLC Medical Directors not working at CLCs involved in the implementation of INTERACT. We will use VA reviewers to facilitate credentialing and access to records. VA staff are more familiar with the VA population and the VA electronic health record. The expert reviewers will be carefully trained in the use of the SIR. [name] has experience in training clinical reviewers in performing SIR. Training will include reviewers independently completing a SIR on standardized practice charts. This will be followed by face-to-face meetings among reviewers to discuss their judgments and to clarify definitions and the information sources necessary to support a particular position viz. the potential "avoidability" of a hospitalization. Practice charts will be reviewed with the group discussion continuing until sources of disagreement have been resolved.

Reviewers will return to their facility where they will be assigned records to review from a nested random sample of the records of 163 residents transferred from the intervention facilities prior to the intervention compared to a nested random sample 163 residents transferred during the supported routine care phase (i.e. after the 6 month training period has been completed). Each reviewer will be asked to review up to 30 charts, each requiring between 45 and 75 minutes. During the initial review period, 25 charts will have a second review to determine inter-rater agreement in the current sample. We will conduct monthly calls with the reviewers to encourage completion of reviews and to clarify questions or issues arising during reviews.

CLC Selection, Matching and Random Assignment: We will match up to 15 pairs of CLCs to ensure at least 8 implement the INTERACT program. Prior to undertaking the facility matching process and in consultation with GEC officials, we may exclude facilities experiencing challenges or management problems that would make them poor intervention candidates. We may also exclude from the matching process CLCs that are atypical or have very high proportions of long stay Veterans with histories of psychiatric conditions, since this population of Veterans has a different profile than our target population and are likely to be hospitalized in an inpatient setting for drastically different reasons.

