Once CLCs are matched, the randomly selected CLC will be approached to solicit their participation with the strong endorsement of GEC leadership. We will approach the randomly selected experimental CLCs until up to 15 have agreed. If a CLC declines to participate, both members of the pair of matched CLCs will be dropped from consideration. The matched “control” case of those CLCs that agree to participate in the INTERACT program will not be approached. The “control” status of a CLC will be known to no one outside of the project research team and will not be divulged in any project description or publication.

Patient Selection: We do not anticipate excluding any Veterans in CLCs from the population to be included in the outcome analyses. The CLC is the unit of random assignment, meaning the intervention changes the skills of CLC staff. For each CLC agreeing to adopt the INTERACT program, it will be as if the CLC is introducing a focused quality improvement program to their staff. As such, no individual patient consent will be requested. We will separately examine hospitalization rates of Veterans classified as long stay or short stay based upon the pattern of recent admission and discharge data, but this will be regardless of their clinical condition or diagnoses.

Outcome Measures: The primary outcome (on which our statistical power estimates were based) will be the **overall hospitalization rate** calculated as the number of admissions to hospital from

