The proposed documentation of the implementation of the INTERACT intervention will have both a quantitative as well as a qualitative component. We will rely upon the data recorded as part of the documentation of the intervention process to characterize the extent of adherence to INTERACT over the course of the training period and across the participating CLC sites. Each site will be characterized in terms of the following: percentage of direct care staff who initiated and completed the on-line training; the percentage of training calls attended by the Champions; the proportion of hospitalizations for which a root cause analysis was completed by the nursing staff; and the number of SBAR and Stop & Watch tools reported on by the Champions per week. To document changes in the intervention from the beginning of the training period to the end of the monitoring period, we will calculate some metrics on a monthly basis to share with the CLC, allowing for the likelihood that the level of adherence of the intervention will change over time, presumably rising throughout the 6 month training period and

beginning to decline during the monitoring period.

The qualitative component of the intervention will be undertaken throughout the monitoring period during the numerous regularly scheduled calls with CLC representatives. An audit trail of anecdotal feedback derived during these calls will be kept in a restricted folder on the SharePoint which only Providence Research staff on this project will have access to.

We are aware the data may be impressionistic and may not accurately reflect the variation in how the intervention was implemented over the duration of the project. However, having information on the utility of the INTERACT tools, how they were used in practice, and how that use changed from the start of the active 6 month training period compared to the 12 month monitoring period will be very valuable in ascertaining fidelity to INTERACT protocols and uptake of intervention. This may help explain possible differential results between facilities.

Aim #4: *To test the effect of the INTERACT intervention on the rate of reduction in hospitalizations from intervention CLCs as compared to the matched control CLCs and to determine via a formalized structured implicit review (SIR) process whether the intervention was associated with a reduction in “avoidable” hospitalizations and that it did not lead to negative outcomes like mortality and ADL decline.*

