Using the results of the Structured Implicit Review process, we will determine the percent of hospital transfers rated as avoidable through better quality of preventive care and early change recognition and the percent rated as inappropriate because the Veteran’s condition could have been safely managed in an average VA CLC. We will compare the percentage hospitalized before the implementation to that after implementation. The sample size of 326 hospitalization records, 163 pre and 163 post-INTERACT, is based upon the assumption that the pre-intervention rate of potentially avoidable hospitalizations will be 40%. For the overall project, we are hypothesizing that there will be a 20% reduction in hospitalizations. Logically, the reductions in hospitalizations will come primarily from the "avoidable" type (otherwise we have a causal inconsistency). Thus, if 40 of 100 hospitalizations pre INTERACT are avoidable and all of the 20% reduction in hospitalizations (20 of 100) will come from among those that are avoidable, we expect a 50% reduction in the rate of avoidable hospitalizations. So, if the pre rate is 40% and the post rate is 20%, using a one tailed test at the alpha .05 level, we need about 100 records

before and 100 after to achieve a power of .90. In the event that some "unavoidable" hospitalizations are really avoided due to the intervention, we increase the sample size to 163 per time period.

Finally, we will test for unintended consequences by examining changes in the rates of overall mortality and in the rate of decline in the late loss ADLs, as measured by the MDS 3.0 nursing home resident assessment, which is done upon admission, periodically thereafter and upon discharge.[45]

Random selection of records with a transfer: A total of 326 medical records with a transfer to the hospital and across the eight intervention CLC sites will be reviewed, 163 pre-INTERACT intervention and 163 post-intervention.

The 163 pre-INTERACT records will be selected from a list of transfers that occurred during the 18 months prior to INTERACT being introduced to the CLCs. This list will be compiled by the study programmer/analysts who will pull it from current CDW data and MDS data. Once the list is generated, random selection will occur to obtain 163 records pre-intervention.

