5. During these qualitative interviews/calls with CLC site Champions intervention staff will review cases where a Veteran had an SBAR completed, but was not transferred to the hospital that subsequently dies and/or is hospitalized within seven days of the documented change in condition record. These cases will be further discussed based upon the content of the SBAR progress note. A standardized set of open ended questions will be asked focusing on whether the Veteran should have been transferred to the hospital sooner, based upon the SBAR progress

note, as well as information about the patients' advanced directives and end of life care wishes. (See Appendix # 6, Interview Guide)

These summarized data will be reported to the DSMB on a quarterly basis. The number of hospitalizations and deaths occurring in the Control group of CLCs will also be reported quarterly and cumulatively (See tables below). Additional aggregate data on outcomes will be provided as requested to confirm the intervention is safe for residents and staff.

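### Aim 4 seeks to show no harm on mortality and ADL decline, but plans only a test of change with no comparator, margin or precision

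*Combined protocol and SAP*

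**What the plan says.** The protocol section on Aim #4 sets out to test the effect on hospitalization and also to determine "that it did not lead to negative outcomes like mortality and ADL decline". The impact statement for the VHA, in the background section, expects that "these reductions in hospitalizations will be achieved without increasing mortality or accelerating functional decline".

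The analysis for this part of the aim is one sentence late in the Aim #4 section: "we will test for unintended consequences by examining changes in the rates of overall mortality". The same sentence adds deterioration in late-loss ADLs, taken from MDS 3.0 assessments. It does not say whether the comparison is before versus after, against matched controls, or both. It gives no model, significance level, sidedness, interval or largest acceptable increase. The difference-in-difference described earlier in the section is written for hospitalization.

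The power work lies elsewhere. Under Outcome Measures: "The primary outcome (on which our statistical power estimates were based) will be the" overall hospitalization rate, and the simulation under Statistical Considerations is for that rate. Aim #4 adds a sample size for the chart review of avoidable transfers. Neither covers mortality or ADL.

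The Data Safety Monitoring Plan has mortality charted against past and concurrent rates in the paired CLCs, quarterly reports of deaths in both arms, and review of residents who die or are hospitalized within seven days of an SBAR note without transfer. Of further outcomes it says: "Additional aggregate data on outcomes will be provided as requested to confirm the intervention is safe for residents and staff".

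**The concern.** Absence of harm is a claim about what the data rule out. A test of change asks whether the data rule out no change. When the test is not significant, the first question is still open, and its answer depends on the width of the interval. The plan gives no interval and no size of harm that it wants to exclude.

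The intervention is meant to let CLC staff manage some acute changes without hospital transfer, so mortality and functional decline are its natural harms. The protocol itself recognises that hospitalizations might be cut too far, and it foresees wider rollout if the programme works. A statement that the reduction came without harm would weigh in that decision. It should rest on a stated precision and not on the lack of a significant result.

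**Working it through.** **Plan's own figure.** There is none for mortality or ADL, so nothing can be reproduced for this claim. The neighbouring closed-form figure does reproduce: the chart review (40% versus 20%, one-sided 0.05, power .90) needs 89 records per period, or 98 with continuity correction, against a stated figure of about 100.

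**Inputs from the protocol.**
- Pairs: "We will match up to 15 pairs of CLCs to ensure at least 8 implement the INTERACT program" (CLC Selection, Matching and Random Assignment), so J = 8 to 15.
- Window: two years before and two years after (Study Procedures, Overview).
- Size: CLCs of at least 50 beds; no mean census or occupancy.

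**Inputs assumed.** Census 60-100 per CLC, 0.2-0.3 deaths per person-year, Poisson variation only, and a difference-in-difference on the log rate.

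**Formulas.** D = J × census × 2 years × death rate (deaths per arm per period). Four such counts enter the contrast, so SE = √(4/D). If the estimate is exactly no change, the upper 95% limit of the rate ratio is exp(1.96 × SE). Power to detect a true 20% rise is P(Z > 1.96 − ln 1.2/SE), with ln 1.2 = 0.182. By symmetry this is also the chance that the upper limit falls below 1.20 when there is no true effect.

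| Pairs | Census, rate | D | SE | Upper limit | Power, 20% rise |
|---|---|---|---|---|---|
| 8 | 60, 0.2 | 192 | 0.144 | 1.33 | .24 |
| 8 | 100, 0.3 | 480 | 0.091 | 1.20 | .51 |
| 15 | 60, 0.2 | 360 | 0.105 | 1.23 | .41 |
| 15 | 100, 0.3 | 900 | 0.067 | 1.14 | .78 |

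**CLC-level variation and few clusters.** Let s be the SD between CLCs of the change in log rate beyond Poisson, and use t on J − 1 degrees of freedom: SE = √(4/D + 2s²/J), upper limit exp(t × SE). A middle case has census 100, 0.2 deaths per person-year and s = 0.1.
- 8 pairs: D = 320, SE = √(0.0125 + 0.0025) = 0.122, t = 2.365, upper limit 1.34. Power to exclude a 20% rise is 25%.
- 15 pairs: D = 600, SE = √(0.0067 + 0.0013) = 0.089, t = 2.145, upper limit 1.21. Power is 48%.

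Over a wider grid (50-150 residents, 0.1-0.4 deaths per person-year, s from 0 to 0.2), 8 pairs give upper limits of 1.16-1.78 and power of 9%-68% to exclude a 20% rise. With 15 pairs the ranges are 1.11-1.47 and 16%-95%.

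**ADL decline.** Assume 15%-30% of residents decline, m = 50-100 assessed residents per CLC and period, and an SD of 0-6 points between CLCs in the change. With SE = √(4p(1−p)/(J·m) + 2s²/J) and t on J − 1 degrees of freedom, the 95% half-width is 6.0-13.0 percentage points with 8 pairs and 4.0-8.6 with 15.

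The 20% rise is only a yardstick for these sums, not a proposed margin.

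**The case against.** A reader might infer that the trial cannot exclude a sizeable harm at any planned size, or that a non-significant result is likely throughout. The documents do not support that. They give no census, death rate or between-CLC variation, and up to 15 pairs are planned. At census 80 and 0.25 deaths per person-year, 15 pairs give D = 600, an upper limit of 1.17 and power of .61 for a 20% rise. With 15 pairs, at least 100 residents per CLC, 0.4 deaths per person-year and little between-CLC variation, the t-based calculation passes 80%.

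The assumed inputs could also be pessimistic. About half of the CLC population is post-acute, so turnover is high and deaths per person-year could exceed 0.3. With 0.4-0.5 and census 100, 8 pairs give D = 640-800 and power of .64-.73. The 24-month baseline is stated as a minimum under Outcome Measures. With an assumed five-year baseline, SE = √(2/D + 2/(2.5D)) = √(2.8/D), and power rises to .33-.67 with 8 pairs and .54-.90 with 15. These objections stand. CLC-level variation works the other way, so the table is not a bound in either direction.

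A reader might also infer that the plan says it will declare safety from a non-significant test. No sentence says so; the gap is that no other rule is given.

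Finally, safety is not unwatched. The DSMB sees deaths in both arms every quarter, and cases are reviewed. That is real mitigation during the trial. It sets no statistical limit, its listed measures do not include ADL, and it does not say how the final Aim 4 conclusion is reached.

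**Conclusion.** The mismatch between aim and analysis holds on the text alone and needs no assumption: a claim of no harm rests on a test of change with no stated comparator, margin or precision. A non-significant change would not support that claim.

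The size is conditional on the assumed census, death rate and variation. On the simple inputs, an estimate of exactly no change leaves rises of about 20%-33% inside the interval with 8 pairs, and about 14%-23% with 15. CLC-level variation and t-based inference widen these; a longer baseline or a higher death rate narrows them. At 8 pairs a material rise would probably not be excluded. At 15 pairs a 20% rise might be. Nothing here suggests that INTERACT is harmful.

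**What to change.** Amend the unintended-consequences sentence in the Aim #4 section as follows.

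- Estimate mortality and ADL decline with the same pair-level difference-in-difference used for hospitalization, and report rate ratios (or differences) with two-sided 95% intervals.
- State that a non-significant result is not evidence of no harm. Conclude that INTERACT did not lead to harm only if the upper limit is below a largest acceptable increase set in advance, separately for mortality and for ADL decline. Otherwise report the size of harm not excluded.
- Have the margins set by investigators who have not seen the between-arm comparison, and record what the DSMB had already seen. The DSMB receives deaths in both arms quarterly and research staff prepare those reports, so neither can be assumed unaware.
- Report ADL decline or death as a supporting analysis, because residents who die have no later ADL score.
- Replace the assumed inputs above with census, death rates and between-CLC variation from the team's historical data, and state the expected interval width.

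Cost: analysis wording and two margins to agree, with no new sites or data collection. The downside is that the safety conclusion may be weaker than the protocol now expects. This is a cheap improvement.

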A second list of transfers will be generated across the intervention CLCs for the post-intervention period and a random selection of 163 of these transfers will also be selected for review.

Once each set of records is selected, the 326 records will be combined and randomized. The randomized list will be randomly divided amongst the reviewers (and include a randomized portion of the records to be used for training on how to complete the SIR).

Reviewer Recruitment and training: Up to 17 physicians or other clinical experts from within the VA and with a geriatric background will be recruited by [name] and her team from LAVAMC. These individuals will be added as study team members and will be required to complete a two-day training (in-person or web based), sign confidentiality and privacy agreement, be provided access through CAPRI (Compensation and Pension Record Interchange) /VistaWeb to the 8 intervention sites through an amendment to the DART DUA for this purpose, provided access to a secure restricted folder within the Providence VA Research Server and access to their secure SharePoint.

To avoid the use of INTERACT influencing the reviewers' structured implicit review we will NOT recruit anyone from our existing CLC intervention sites.

After the reviewers complete their assigned chart reviews they will participate in a debriefing with the LA team, notifying them about the use of INTERACT as the QI intervention and the impact their reviews will have on determining INTERACT's effectiveness at preventing 'avoidable' hospitalizations from occurring within the CLCs.

The reviewers will be trained to use CAPRI/VistaWeb to complete the chart reviews. CAPRI/VistaWeb provides a standardized, user-friendly method to access the charts for review within VA.

Structured Implicit Review (SIR) Procedure: Each reviewer will be randomly assigned an equal percent of the 326 charts to review based on the number of reviewers. The charts will be randomly assigned, from across the intervention sites to the reviewers. The reviewers will not be provided any specific information about the intervention conducted using INTERACT or any indication of whether it was a pre or post intervention chart.

The reviewers' will then complete their review of the charts using the SIR Instruction Manual and Guide (See Appendix 7, Structure Implicit Review Instructions and Guide). They will utilize access to a

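### Dealing review charts by period and stratifying the pre/post comparison by reviewer would take reviewer strictness out of the error at almost no cost

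*Combined protocol and SAP*

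**What the plan says.** All references are to the combined protocol and SAP.

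- **Sample.** Aim #4 sets "The sample size of 326 hospitalization records, 163 pre and 163 post-INTERACT".
- **Dealing.** Under the paragraphs on random selection of records: "Once each set of records is selected, the 326 records will be combined and randomized". Then: "The randomized list will be randomly divided amongst the reviewers". The Structured Implicit Review (SIR) Procedure gives each reviewer an equal share, with up to 17 reviewers, and keeps from them whether a chart is pre or post.
- **Comparison.** Aim #4 states: "We will compare the percentage hospitalized before the implementation to that after implementation". The sentence before it shows that the percentages meant are those of transfers rated avoidable or inappropriate. No model and no reviewer term is named. Outcome Measures describes the final SIR variable as ordinal.
- **Reviewer agreement.** The section on implicit review of potentially avoidable hospitalizations trains reviewers on practice charts until disagreements are settled, caps the load at 30 charts each, and adds that "25 charts will have a second review to determine inter-rater agreement in the current sample". No use of that agreement result in the comparison is stated.

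**The concern.** Implicit review rests on clinical judgement, and the training and double reviews show that the authors expect some disagreement. With about 19 charts each and no balance by period, a strict reviewer may hold mostly pre charts and a lenient one mostly post charts, or the reverse. A comparison of two pooled percentages leaves that chance confounding in the error. The review is the plan's only direct test of whether avoidable transfers fell, and its sample is fixed and costly in reviewer time, so precision that costs nothing is worth having.

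**Working it through.** **1. The plan's own figure.** Inputs from Aim #4: "So, if the pre rate is 40% and the post rate is 20%, using a one tailed test at the alpha .05 level", with about 100 records "before and 100 after to achieve a power of .90". With mean rate .30:

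n = [1.645·√(2·.30·.70) + 1.282·√(.24 + .16)]² / .20² = (1.066 + 0.811)² / .04 ≈ 88, or 89 rounded up.

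With the continuity correction, n = (88.0/4)·[1 + √(1 + 4/(88.0·.20))]² ≈ 98. The stated figure of about 100 reproduces.

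**2. Power at 163 per period (one-sided .05, uncorrected).**
- 40% v 20%: z = (.20·√163 − 1.645·√.42)/√.40 = (2.553 − 1.066)/.632 = 2.35; power .99.
- 40% v 25%: z = (.15·√163 − 1.645·√.43875)/√.4275 = (1.915 − 1.090)/.654 = 1.26; power .90.

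The 25% is an assumption. The protocol raises n from about 100 to 163 to allow for a weaker effect but does not state the rate it has in mind.

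**3. Imbalance under the current deal.** 326/17 ≈ 19 charts per reviewer. The SD of one reviewer's pre count is √(19·.25·307/325) = 2.12, so the pre-minus-post count has SD 4.2. By the hypergeometric distribution, a split of 13:6 or worse has probability about .15 for any one reviewer. In simulation the worst imbalance among 17 reviewers averages about 9 charts.

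**4. Where reviewer variation sits.** If reviewer r rates a proportion p_r as avoidable and p is the mean of p_r, the variance of one rating is

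p(1 − p) = mean of p_r(1 − p_r) + variance of p_r.

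The two-proportion formula uses the left side, so reviewer variation is already counted in the sample size. Stratifying by reviewer removes the last term.

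**5. Size of the gain.** Simulation: 6,000 runs per setting, 163 + 163 charts, 17 reviewers, logistic model with a random reviewer intercept, overall rates held at 40% v 25%, one-sided .05. *Current* is the unbalanced deal with a crude test; *proposed* is the balanced deal with a Mantel-Haenszel test by reviewer. The reviewer SD is assumed.

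| Reviewer SD (logit) | ICC at 40% | SD of difference, current → proposed | Variance reduction | Power, current → proposed |
|---|---|---|---|---|
| 0 | 0 | .0516 → .0513 | 1% (noise) | .898 → .895 |
| 0.5 | .05 | .0519 → .0504 | 6% | .897 → .912 |
| 1.0 | .17 | .0528 → .0491 | 14% | .894 → .933 |
| 1.5 | .29 | .0532 → .0468 | 23% | .895 → .957 |

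Variance reduction is 1 − (proposed/current)²; for SD 1.0, 1 − (.0491/.0528)² = .135. The Monte Carlo standard error of a power near .90 is √(.9·.1/6000) ≈ .004. Across repeated simulations the reductions are about 5%, 15% and 22-28% at SD 0.6, 1.0 and 1.5.

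At 40% v 20%, over the same four SDs, power goes .990 → .990, .990 → .992, .989 → .996 and .988 → .999.

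With 11 reviewers, the fewest the 30-chart cap allows (326/30 = 10.9), SD 1.0 gives .895 → .937 at 40% v 25%.

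**6. Level, and the two parts taken separately.**
- Current plan: simulated type I error of the crude test .048 to .055.
- Balanced deal with a crude test: .035 at SD 1.0 and .026 at SD 1.5, so conservative.
- Current deal with reviewer strata: power at 40% v 25% of .921 (SD 1.0) and .949 (SD 1.5), which is most of the gain, but .884 against .898 when reviewers do not differ.

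**The case against.** The case for leaving the plan alone is fair. Charts are dealt at random to masked reviewers, so the comparison is valid. The stated effect already has power of about .99. Two-day training, a common manual, consensus on practice charts and monthly calls should shrink reviewer differences, and at a small SD the gain is one or two points of power. An SD of 1.5 after such training would be extreme. The absence of a reviewer term is also an inference from silence, since no model is given and nothing rules one out. All of this stands, and it limits the point to efficiency.

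Two stronger readings are tempting. The first is that uneven dealing biases the result. It does not: the imbalance is random with respect to strictness and the test keeps its level.

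The second is that the review is underpowered. If 40% and 25% are taken as the rates of the median reviewer, simulated power of the current plan drops to .86, .80 and .69 at SDs of 0.6, 1.0 and 1.5. But the overall rates are then 40.7 v 26.5, 41.7 v 28.6 and 42.9 v 31.4, so at SD 1.5 the true difference is 11.5 points, not 15. The drop comes mainly from that smaller difference, not from how charts are dealt. Aim #4 states its rates as percentages of all hospitalizations; with those held fixed, current power stays near .90.

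What the objection does not meet is that training reduces reviewer differences and the 25 double reviews measure them, but neither takes them out of the comparison.

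**Conclusion.** The point holds as a small forgone gain in precision. It is neither a bias nor a shortfall in power. If reviewers differ, dealing by period and stratifying by reviewer cuts the variance of the pre/post difference by about 5% to 28% over assumed logit SDs of 0.6 to 1.5. At an assumed weaker effect of 40% v 25% that lifts power from about .90 to between .91 and .96. At the planned effect the gain is at most about one point. If reviewers do not differ, nothing is gained and nothing material is lost. These sizes rest on a reviewer variance that the documents do not give, on overall rates held fixed, and on 17 reviewers with equal shares.

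**What to change.** Make both changes together.

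1. The programmer, who knows the period, deals the pre and post lists separately so that each reviewer has equal numbers of each (within one), in shuffled order. Reviewers stay masked and are told nothing of the split.
2. Pre-specify the pre/post comparison as stratified by reviewer: Mantel-Haenszel for the percentages, or a logistic or ordinal model with a reviewer term.

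If charts have already been dealt, add the reviewer term alone. It recovers most of the gain, at a cost of about 1 point of power if reviewers turn out not to differ.

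Cost: one change to the allocation program and one line in the analysis plan. No extra charts, reviewers or unmasking are needed.
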